6.7 Protocol Deviations

Prior to database lock, AMO Pharma will review the individual deviations to confirm that important protocol deviations have been captured correctly (as defined in section 6.4 above) and to agree impact to analysis sets as indicated in the Protocol Deviation Criteria (PDC) form.

Only important protocol deviations, as specified in the PDC form, will be included in the statistical outputs.

Details of important protocol deviations (date, deviation category and specific details) and subject eligibility will be listed.

The number and percentage of subjects with at least one important protocol deviation will be summarised for each deviation category.

6.8 Background and Demographic Characteristics

6.8.1 Demography

Demographic characteristics (age, sex, ethnic origin and race), body measurements (height, weight and BMI), dominant arm (left or right) and number of CTG repeats (if available) collected at Screening will be summarised overall and by site. In addition, date of birth (DOB) will be listed. Subjects enrolled in New Zealand will have a DOB captured as 01 MMM YYYY.

Age is calculated in years from the date of the screening visit.

All subject demographic data including informed consent/assent will be listed.

6.8.2 Medical History

Medical and surgical history events will be coded using the Medical Dictionary for Regulatory Activities (MedDRA) dictionary version applicable at eCRF go-live. The version used will be indicated in the data summaries and listings. Previous and ongoing conditions will be presented separately. Previous conditions are defined as those that started and ended prior to the first administration of study treatment, including . All other conditions will be assumed ongoing.

The number and percentage of subjects will be presented by system organ class (SOC), and preferred term (PT), where SOC and PT will be presented in decreasing frequency of the total number of subjects with medical or surgical history events. In summary tables, subjects with medical or surgical history in the same SOC or having the same preferred term recorded multiple times will be counted only once for that SOC and PT.

All events will be listed.

6.8.3 Symptoms of Disease

Each symptom of disease under study is captured as free text with a start date and severity (mild/moderate/severe). All symptoms of disease under study data will be coded using the MedDRA dictionary applicable at eCRF go-live with the MedDRA version used being indicated.

All symptoms of disease data will be listed. The MedDRA version used will be indicated.

6.8.4 Caregiver DM1 Status

Caregiver DM1 status data will be listed.

6.8.5 Other Data

sampling data, test telehealth session data and telehealth type data will be listed.

6.9 Prior, Concomitant and Follow-up Period Medications

Medications will be coded using the latest World Health Organization (WHO) Drug dictionary version applicable at eCRF go-live. The version used will be indicated in the data summaries and listings.

Prior medications are defined as those that started and ended prior to the first administration of randomized study treatment. Medications that ended on or before a subject's last dose of randomized study medication and are either ongoing at the first administration of randomized study treatment or started after the time of first administration will be deemed to be concomitant medications. If medication dates are incomplete and it is not clear whether the medication was concomitant, it is assumed to be concomitant. Follow-up period medications are defined as those that started after a subject's last dose of randomized study medication.

Prior, concomitant and follow-up period medications will be summarized separately.

[figure not shown]
The number and percentage of subjects taking medications will be summarised by medication class and standardised medication name, where medication class and standardised medication name will be presented in decreasing frequency of the total number of subjects with medications. In summary tables, subjects taking multiple medications in the same medication class or having the same standardised medication recorded multiple times in the study will be counted only once for that specific medication class and standardised medication name.

Medication data will be listed, where medications will be flagged as prior, concomitant or follow-up period medications.

[figure not shown]

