9.9 Permitted concomitant medication/ non- pharmacological therapies

All concomitant medications and non-pharmacological therapies (e.g. physiotherapy, occupational therapy, speech therapy, yoga) taken or implemented during the study will be recorded in the CRF with indication, dose information, frequency and dates of administration as applicable. The Investigator should inquire at each clinic visit whether there have been changes in any permitted concomitant medications or non-medical therapies or interventions, including those in the school setting (e.g. speech therapy).

With regard to any permitted medication (e.g. concomitant mexiletine or stimulants) or therapy (e.g. occupational or physiotherapy) that the subject was taking on entry to the study, every effort should be made to continue at the same dose (as applicable) and frequency throughout the study.

AMO Pharma Ltd.

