2.2 Study Estimands

Following the adoption by FDA of ICH E9 R1 addendum on estimands and sensitivity analyses, the following estimands have been defined.

The estimand for the primary efficacy endpoint is the difference between group means in the change from baseline in total score on the Clinician-Completed Congenital DM1 Rating Scale (CDM1-RS) at end of treatment (EOT).

Estimand components (Combined approach):

- A. The population is defined through appropriate inclusion/exclusion criteria to reflect the targeted patient population.
- B. The variable is the change from baseline in CDM1-RS total score at EOT.
- C. The intervention effect of subjects who discontinue treatment or discontinue the study due to AE/ death will be calculated based on available data up to the time of study discontinuation.
- D. The population-level summary measure is the difference between adjusted group means in the change from baseline in the CDM1-RS at EOT.

The introduction of new physical therapy, use of permitted concomitant medication and non-compliance to protocol (e.g., poor treatment adherence, use of prohibited medication and other protocol deviations) are assumed to be well-balanced events across both arms and should not affect the estimation of the treatment effects. Therefore, in the first instance all observed data will be used regardless of the occurrence of these intercurrent events. In-clinic visits are of primary interest. If a subject's in-clinic visit is unavailable due to COVID-19, the data will be imputed with the corresponding telehealth assessment.

Missing data due to early study discontinuations or missed visits (where both in-clinic and telehealth are missed) are assumed to be Missing-At-Random (MAR) and will not be imputed. Instead, a direct likelihood approach such as a Mixed Model Repeated Measures (MMRM) will be used to analyze the available data.

Sensitivity and supplementary analyses will assess the robustness of the primary analysis to these chosen strategies and will address the occurrence and potential imbalance of intercurrent events, deaths and COVID-19 impacts between treatment groups.

The secondary estimand for the study is CGI-I at EOT:

The estimand for the key secondary efficacy endpoint is the difference between treatment means in the observed CGI-I score at EOT.

Estimand components (Combined approach):

- A. The population is defined through appropriate inclusion/exclusion criteria to reflect the targeted patient population.

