- Improvement during the run-in period (Yes, No). Improvement in this case is defined as a 2-point or greater improvement in the total score.
- To identify items which are primarily driving an improvement in CDM1-RS total score, the 11 individual items will each be analysed in an analogous method to the primary estimand above. A forest plot with all 11-items on the y-axis, showing the treatment effect will additionally be provided.
- The occurrence and potential imbalance of intercurrent events (e.g. concomitant medication changes, protocol non-compliance), deaths and COVID-19 impacts between treatment groups will be reviewed after unblinding the randomization.
 - If an imbalance is detected in the intercurrent events, further summaries and/or analyses may be undertaken to assess the impact of this.
 - Deaths are not anticipated during the study. If an imbalance in deaths is determined, a joint rank analysis (based on the change in CDM1-RS from baseline and time to death) may be utilized.

Summaries and Figures

Summary statistics of observed values and change from baseline will be presented by visit and treatment for the in-clinic and telehealth visits separately. For subjects who have both an in-clinic and telehealth assessment at a visit, change from baseline in CDM1-RS will be calculated for both methods and summarised separately.

The observed CDM1-RS total score will be presented over time using by subject line plots by treatment group for the in-clinic and telehealth visits separately. The plots will be presented together but on two separate panels.

Additionally, histograms of the change from baseline at each visit will be presented by treatment group. Empirical cumulative distribution functions (CDFs) of the change from baseline will be presented by treatment group at Visit

The adjusted LS mean changes from baseline and SEs over time will be presented via line plots as estimated by the primary estimand MMRM model by treatment group.

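### As written, SAP 6.9 gives no category to a drug taken during randomized treatment and continued past the last dose, so the by-arm concomitant table under-counts

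*SAP*

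**What the plan says.** SAP 6.9 defines three categories by reference to the randomized dosing period.

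- **Prior:** both start and stop fall before the first randomized dose.
- **Concomitant:** "Medications that ended on or before a subject's last dose of randomized study medication and are either ongoing at the first administration", or begun after that first dose.
- **Follow-up:** "Follow-up period medications are defined as those that started after" the last randomized dose.

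There is one default: "If medication dates are incomplete and it is not clear whether the medication was concomitant, it is assumed to be concomitant". Each category gets its own summary, and SAP 6.5 has tables presented by treatment group. The listing uses the same three labels: "Medication data will be listed, where medications will be flagged as prior, concomitant or follow-up period medications".

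Two other parts of the SAP concern concomitant medication. Section 2.2 names permitted and prohibited medication among the intercurrent events that "are assumed to be well-balanced events across both arms and should not affect the estimation of the treatment effects". Section 6.13.1.1 plans a review, after unblinding, of imbalance between arms in such events, with changes in concomitant medication as an example.

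On regimens the child was already taking at entry, Protocol 9.9 says that "every effort should be made to continue at the same dose (as applicable) and frequency throughout the study".

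**The concern.** The stop-date condition comes first in the concomitant sentence and governs both of its branches. A drug can be taken on every day of randomized treatment and still fail the definition because it did not stop in time. It is not prior either, and it is not follow-up, because it started too early.

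This is an expected pattern. Protocol 9.9, and exclusion criterion 3 in Protocol 7.3, ask that permitted regimens be kept stable to the end of the study. For a child who has the post-treatment follow-up period, a regimen kept stable as asked runs past the last dose. A drug started on treatment, for example for an adverse event, and then continued falls into the same gap.

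Two outputs are at stake. The concomitant table by arm would omit drugs that children were taking, and the listing would require a flag that does not exist for them. That weakens the table as support for the balance assumption in SAP 2.2, and for the review in 6.13.1.1 if the review draws on it. New drugs started on treatment and continued matter most here, since stable entry drugs are a question of baseline balance.

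**Working it through.** The plan states no figure to reproduce; the check is whether the three definitions cover every case.

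**Inputs, all from SAP 6.9.** Let S be the start, E the stop, F the first and L the last randomized dose.

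- Prior: S < F and E < F.
- Concomitant: E ≤ L, and either ongoing at F or S after F.
- Follow-up: S > L.

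**Step 1: enumerate.** Three start positions are crossed with four stop positions, and impossible pairs (stop before start) are dropped. This leaves 4 + 3 + 2 = 9 patterns.

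| Start | Stop | On treatment? | SAP 6.9, literal | Blank stop treated as incomplete | Overlap rule |
|---|---|---|---|---|---|
| Before F | Before F | No | Prior | Prior | Prior |
| Before F | F to L | Yes | Concomitant | Concomitant | Concomitant |
| Before F | After L | Yes | None | None | Concomitant |
| Before F | Ongoing | Yes | None | Concomitant | Concomitant |
| F to L | F to L | Yes | Concomitant | Concomitant | Concomitant |
| F to L | After L | Yes | None | None | Concomitant |
| F to L | Ongoing | Yes | None | Concomitant | Concomitant |
| After L | After L | No | Follow-up | Follow-up | Follow-up |
| After L | Ongoing | No | Follow-up | Follow-up | Follow-up |

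- Literal reading: prior 1, concomitant 2, follow-up 2, none 4. So 4 of the 6 on-treatment patterns have no category.
- Blank stop treated as incomplete: prior 1, concomitant 4, follow-up 2, none 2. So 2 of 6 have no category.
- Overlap rule: prior 1, concomitant 6, follow-up 2, none 0.

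**Step 2: cross-check on dates.** Take an illustrative calendar of days 1 to 30 with F = day 10 and L = day 20, and every pair with S ≤ E.

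- All pairs: 30 × 31 / 2 = 465.
- Prior (both dates in days 1 to 9): 9 × 10 / 2 = 45.
- Follow-up (both dates in days 21 to 30): 10 × 11 / 2 = 55.
- No category (start in days 1 to 20, stop in days 21 to 30): 20 × 10 = 200.
- Concomitant: 465 − 45 − 55 − 200 = 165.

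Every unclassified pair has S ≤ L and E > L. Under the overlap rule the concomitant count becomes 165 + 200 = 365, and 45 + 365 + 55 = 465, so each pair falls in exactly one category. The grid locates the gap; it does not estimate how many records are affected.

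**Step 3: does other text close the gap?** The default needs dates that are incomplete and a status that is unclear. A recorded stop date after L is neither. SAP 6.18 does not mention medication categories, the SAP addendum does not revise 6.9, and the protocol has no competing definition. For comparison, the medical-history rule in SAP 6.8.2 has a catch-all ("All other conditions will be assumed ongoing"); 6.9 has none.

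**The case against.** The strongest case against accepts the gap in the wording but disputes how much follows from it.

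- **Programming is not visible.** Shells are in a separate document and no code is given. A programmer may have used a sensible rule, or sent every blank stop date to concomitant through the default. Long-term drugs are probably the ones marked ongoing, so the default could recover much of the gap. This stands as a limit on what is known about the actual tables. It does not rescue the written rule, and a recorded stop after the last dose stays outside on any reading.
- **Descriptive effect only.** No model, analysis set or sensitivity analysis uses these categories, every record is still listed, and the CRF holds dose, frequency and dates. This stands in full.
- **Loose link to the imbalance review.** That review concerns changes in medication. A table counting each child once per drug name would not show a dose change even under a corrected rule. New physical therapy sits in the same balance assumption, yet SAP 6.10 only lists non-pharmacological therapy. The SAP does not say the review uses this table. This stands, and it is why the efficacy consequence is conditional. New drugs started on treatment would, however, appear in a correct table.
- **Pattern counts say nothing about frequency.** Correct. Because each child counts once per drug, another ended record of the same drug reduces the under-count further.

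**Conclusion.** The concern holds. Followed as written, SAP 6.9 leaves a drug started on or before the last randomized dose and known to continue past it in no category. It drops out of the concomitant table, and no permitted listing flag describes it. The gap covers 4 of 6 on-treatment patterns on a literal reading, and 2 of 6 if a blank stop date is taken as incomplete; the SAP does not say which handling applies.

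The number of records or children affected cannot be derived from the documents, and whether issued tables are wrong depends on what was programmed. The primary and key secondary results are unaffected. The conclusion assumes that the definition paragraph is complete as it reads; the gaps left by missing figures in that section fall after it.

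**What to change.** Replace the concomitant definition in SAP 6.9 with an overlap rule: a medication is concomitant if it started on or before the last randomized dose and either stopped on or after the first randomized dose or is ongoing. Leave prior and follow-up unchanged.

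Add two clarifications:

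1. A medication marked ongoing with a blank stop date has a known status and is not an incomplete date.
2. Concomitant drugs that continue past the last dose carry an additional flag in the listing and are not excluded from the table.

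If tables already exist, state which rule was programmed and re-run the medication summaries if it was the literal one.

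The cost is one replacement sentence and the clarifications in the SAP, one line of derivation code, and at most a re-run of the medication summary tables. No efficacy analysis has to be repeated.

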6.10 Non-Pharmacological Treatment Therapies

Non-Pharmacological treatment therapy data will be listed.

[figure not shown]
6.11 Administration of Study treatment and Exposure

Date:22FEB2023 Version: Final 2.0 ST/form/010/15

The total amount (mg) of randomized treatment expected to be taken is derived as follows:

Date of last dose of randomized treatment— date of first dose of randomized treatment + 1. Any stideglusib/matched placebo received during should be excluded.

the number of subjects that were

The above derived variables and study drug dispensing, study drug return, study drug and subject diary card information will be listed.

6.12 COVID-19 Impact to study

Due to the global COVID-19 (Coronavirus Disease 2019) pandemic and the potential for resurgences of COVID-19, for the purposes of this protocol, 'in-clinic' visits, when pertaining to Visits -Visit (Weeks), may be conducted via a combination of telehealth and home healthcare providers for COVID-19 related reasons e.g. institutional restrictions, travel restrictions, quarantine or shielding prevent subjects from being seen in-person at the investigator site.

Subjects who have completed Screening (Visit but are unable to attend Run-In (Visit in-person due to COVID-19 related reasons will be allowed the opportunity to rescreen for the study if study enrolment is still ongoing once they are able to attend the clinic again in person. These subjects will have a new screening number and will be treated as a separate subject in the tables and listings. Subjects who have attended the Run-In (Visit and are unable to attend the Baseline (Visit in-person due to COVID-19 related reasons will be discontinued and replaced.

All subjects are expected to have an in-clinic visit for all pre-specified timepoints (except for the collection of AE and concomitant medication data at Visits and Should an in-clinic visit be missed the corresponding telehealth visit and/or home health care visit can replace it. Additionally, there will be 3 occasions in the study (Visit and Visit and Visit where dual telehealth and in-clinic assessments will be conducted. To evaluate the consistency of telehealth data and in-clinic data for the CDM1-RS and CGI rating scales and to minimize the potential bias, Visits and are performed using both in-clinic and telehealth data collection approaches. Sensitivity analyses to evaluate the consistency of these two methods of data collection is provided in sections 6.13.1 and 6.13.2.

It is noted that particular attention may need to be given to the impact on key efficacy or safety assessments as a result of the COVID-19 pandemic. Consideration of the different areas of impact has been made as described below:

- Important protocol deviations related to COVID-19 will be recorded under the
 deviation category of 'Other' with a free text reason indicating the deviation was
 due to COVID-19. The assigned categories will be presented in the protocol
 deviation listing and table summary of important deviations as described in
 section 6.7.
- Subjects who prematurely discontinue the study due to COVID-19 will be identified as described in section 6.6 and will be presented as a reason for withdrawal of 'COVID-19'.
- Missing efficacy data for the primary and key secondary estimands will be subject to the imputation and analysis methods described in sections 6.13.1 and 6.13.2.

In order to provide supportive information for interpretation of the key efficacy and safety analyses, a summary of the number and percentage of subjects with missing in-clinic (telehealth assessment only being available) and completely missing assessments (no in-clinic or telehealth assessment being available) at each scheduled visit will be presented by treatment group and overall for the following selected data on the ITT analysis set or safety analysis set (safety data) as appropriate:

- Primary and secondary efficacy endpoints (specifically in-clinic and telehealth Clinician Completed CDM1-RS, clinician in-clinic and telehealth CGI-I, Top 3 Caregiver concerns, Caregiver Completed CDM1-RS, 10-meter walk-run test)
- Clinical chemistry and complete blood counts
- ECGs

A summary of missing items for the clinician in-clinic and telehealth CDM1-RS and caregiver CDM1-RS will also be produced.

If these summaries suggest that further investigation is beneficial, additional summaries and/or analyses may be added post hoc to address missing data or assessments outside of protocol defined windows. This may include but is not limited to: additional sensitivity analyses of the efficacy endpoints, additional summaries of selected safety data for overall worst case post-baseline values, application of visit windows to group post-baseline data across multiple visits as appropriate.

6.13 Efficacy Evaluation

Unless specified otherwise, all listings will be based on the RIS set.

All efficacy analyses and summaries will be primarily performed on the ITT analysis set. Summaries of run-in efficacy data will also be performed on the RIS set. The analysis for the primary and key secondary estimands will be repeated on the FAS and the PPS sets. The sensitivity analyses of the primary and the key secondary estimands will be based on the ITT set only. All other efficacy analyses will be based on the ITT set only.

All hypothesis tests comparing tideglusib and placebo will be two-sided and conducted at the 5% significance level, unless otherwise specified.

6.13.1.1 Primary Estimand and Supplementary Analysis

The estimand for the primary efficacy endpoint is the difference between group adjusted means in the changes from baseline in CDM1-RS total score at EOT.

If a subject's in-clinic visit is unavailable, the data will be imputed with the corresponding telehealth assessment. The use of telehealth assessments is thought unlikely to be related to outcome, however, it will be assessed for balance between the treatment groups and sensitivity analyses may be conducted in the event of imbalance.

The null hypothesis being tested for the primary endpoint is that there is no difference in mean change in CDM1-RS total score from baseline to EOT between the tideglusib and placebo treatment groups:

$$H_0$$
: Mean Change_{tideglusib} = Mean Change_{placebo}

The alternative hypothesis is that there is a difference in either direction in the mean change in CDM1-RS total score from baseline to EOT between the tideglusib and placebo treatment groups:

$$H_1$$
: Mean Change_{tideglusib} \neq Mean Change_{placebo}

The analysis will include data from Visit (randomisation) to Visit (EOT) inclusive. Data from other visits will be included in the summaries and listings.

Primary Analysis

The primary estimand will be analysed using a mixed model for repeated measures (MMRM).

The treatment difference between tideglusib and placebo at Visit (EOT) will be estimated as the simple contrast in the treatment effect. The standard error (SE), p-value and 2-sided 95% confidence interval (CI), based on the difference in the Least Squares (LS) means between the two treatment groups will be presented. The LS Means, SE and 95% CI will additionally be presented for each treatment by visit.

The MMRM model will be implemented using restricted maximum likelihood (REML). The Kenward-Roger approximation will be used to estimate the denominator degrees of freedom and standard errors

Initially an unstructured covariance matrix will be investigated. If this analysis fails to converge, the following alternative structures will be tested in the following order until convergence is achieved: Toeplitz, AR(1) and compound symmetry. If a covariance matrix other than unstructured is selected, the estimated standard errors and variance-covariance matrix of the fixed-effects parameters will be computed using a robust "sandwich" estimator (i.e., by specifying the EMPIRICAL option on the PROC MIXED statement).

The model will contain treatment, age group, visit and treatment by visit interaction as fixed effects, baseline CDM1-RS as a covariate.

If the baseline CDM1-RS and/or age group is not significant at the 15% level (i.e., p>=0.15) then a secondary analysis will be conducted with the term(s) removed from the model. Similarly if the p-value for the treatment by visit interaction is not significant at the 15% level, that term will be removed in the secondary analysis and the LS

Date:22FEB2023 Version: Final 2.0 ST/form/010/15 Means and treatment differences under the assumption of a constant treatment effect over time will be estimated.

Normality of the data will be investigated through plots of the residuals. Non-parametric analyses may additionally be performed if the data are found to be sufficiently non-normal. This will include non-parametric analysis of covariance (ANCOVA) (Koch G.G. et al, 1998 and Zink, R. and Koch, G.G., 2012) of the change from baseline to Visit with treatment, baseline CDM1-RS and age group as covariates.

Any data collected after study discontinuation will not contribute to the treatment effect estimate. Only data up to study discontinuation will be used.

Missing Data

Missing data due to early study discontinuations or missed visits are assumed to be missing at random (MAR) and observed data only will be used for the primary analysis. The MMRM accounts for these missing data using a direct likelihood approach.

Sensitivity Analysis

Several sensitivity analyses will be applied to this endpoint:

Sensitivity analysis 1 – Multiple Imputation: Missing at Random (MAR)

At a visit, if a subject has no in-clinic or telehealth assessment data the visit is assumed to be MAR. This assumes that subjects with missing data follow the same trajectory as other subjects in their respective treatment arm that have complete data.

- Intermittent missing data will first be imputed using the MCMC method, appropriate for non-monotonic missing data.
- Data missing after subjects discontinue the study early will be imputed using a regression, appropriate for monotone missingness. At each time point, missing data will be assumed to follow a distribution similar to scores for subjects who are still in the study and randomized to the same treatment group.

The MI method (as described in Section 6.3) will be employed with the following assumptions/steps:

- Covariates that may be used in the MI will include treatment group, age group and baseline CDM1-RS.
- 20 imputations will be completed.
- Seed number and covariates used for imputation will be agreed prior to data base lock and detailed in the TFL outputs.

The MMRM will be applied to each of the multiply imputed data sets, as described above for the primary estimand. The estimates from these models will then be combined using Ruben's (1987) rule and analysed to provide the endpoint estimates and summarized.

Sensitivity analysis 2 – Single Imputation: WOCF

At a visit, if a subject has no in-clinic or telehealth assessment data the visit is assumed to be MAR. This assumes that the trajectory of subjects who discontinue the study follows that of their worst observation. Worst Observation Carried Forward (WOCF)

will be used and the MMRM as described above for the primary estimand will be applied to these data.

Sensitivity analysis 3 – Multiple Imputation: In-clinic visits only

At a visit, if a subject has a telehealth assessment and no in-clinic assessment the visit is assumed to be MAR. Modelling in-clinic visits only (sensitivity analysis 3) is deemed a more valuable analysis than modelling telehealth visits only (sensitivity analysis 4).

- Intermittent missing data for in-clinic visits will first be imputed using the MCMC method, appropriate for non-monotonic missing data.
- Data missing after subjects discontinue the study early will be imputed using a regression, appropriate for monotone missingness. At each time point, missing data will be assumed to follow a distribution similar to scores for subjects who are still in the study and randomized to the same treatment group.

The MI procedure will be employed as described for sensitivity analysis 1. The MMRM will be applied to the multiply imputed data sets, as described above for the primary estimand. The estimates from these models will then be combined using Ruben's (1987) rule and analysed to provide the endpoint estimates and summarized.

Sensitivity analysis 4 – Multiple Imputation: Telehealth visits only

At a visit, if a subject has an in-clinic assessment and no telehealth assessment the visit is assumed to be MAR.

- Intermittent missing data for telehealth visits will first be imputed using the MCMC method, appropriate for non-monotonic missing data.
- Data missing after subjects discontinue the study early will be imputed using a
 regression, appropriate for monotone missingness. At each time point, missing
 data will be assumed to follow a distribution similar to scores for subjects who
 are still in the study and randomized to the same treatment group.

The MI procedure will be employed as described for sensitivity analysis 1. The MMRM will be applied to the multiply imputed data sets, as described above for the primary estimand. The estimates from these models will then be combined using Ruben's (1987) rule and analysed to provide the endpoint estimates and summarized.

Sensitivity analysis 5 – Completers

The MMRM will be applied to all subjects who have completed the study to EOT.

Sensitivity Analysis 6 – Rank Analysis

The change from baseline in CDM1-RS total score at EOT will be ranked with any tied observations being assigned an average rank. The sum of the ranks for each treatment will be calculated. The non-parametric Wilcoxon rank-sum test will be utilised at a 2-sided 5% level of significance to test the null hypothesis that the distribution of post randomization CDM1-RS total score values for tideglusib and placebo is equal against the alternative hypothesis that the distribution of post-randomization CDM1-RS total score values for tideglusib and placebo are not equal. The Hodges-Lehmann estimate of the difference between the two treatments and 95% confidence interval will also be calculated.

Sensitivity analysis 7 – Multiple Imputation: MNAR control-based pattern

For this analysis, in-clinic and telehealth data will be used as for the primary analysis.

- Intermittent missing data for in-clinic visits will first be imputed using the FCS method, appropriate for non-monotonic missing data.
- Data missing after subjects discontinue the study early will be imputed using a regression, appropriate for monotone missingness. At each time point, missing data will be assumed to follow a distribution similar to scores for subjects who are still in the study and randomized to placebo.

The MI procedure will be employed as described for sensitivity analysis 1. The MMRM will be applied to the multiply imputed data sets, as described above for the primary estimand. The estimates from these models will then be combined using Ruben's (1987) rule and analysed to provide the endpoint estimates and summarized.

Sensitivity analysis 8 – Multiple Imputation: MNAR delta-adjustment pattern

For this analysis, in-clinic and telehealth data will be used as for the primary analysis.

- Intermittent missing data for in-clinic visits will first be imputed using the FCS method, appropriate for non-monotonic missing data.
- Data missing after subjects discontinue the study early will be imputed using a regression, appropriate for monotone missingness. At each time point, missing data will be assumed to follow a distribution similar to scores for subjects who are still in the study and randomized to the same treatment group. However, a fixed 5% worsening (delta-adjustment) to the outcome in the tideglusib group will then be applied.
- In the event of a statistically significant treatment effect, several deltaadjustments will be performed until non-significance occurs. This will be used to identify how much worse a response would need to have occurred in the subjects with missing data in order to have overturned the significant result (a tipping-point analysis).

The MI procedure will be employed as described for sensitivity analysis 1. The MMRM will be applied to the multiply imputed data sets, as described above for the primary estimand. The estimates from these models will then be combined using Ruben's (1987) rule and analysed to provide the endpoint estimates and summarized.

Supplementary Analysis

- The primary efficacy analysis will be repeated on the FAS and PPS.
- The proportion of subjects who have a 10% or greater improvement over baseline in the CDM1-RS total score will be summarised and compared using a Fishers Exact test. Similar analyses using 15% and 20% or greater improvements will also be undertaken.
- Subgroup analyses will be performed by key baseline characteristics. The balance between treatment groups will be assessed and if any are evaluated as not being consistent a respective covariate will be included in the MMRM. For each subgroup, the main effect, treatment-by-subgroup interaction and treatment by visit by subgroup interaction terms will be added to the model. Any interactions that are statistically significant at the 15% level for the end of treatment visit will have their nature described. These models will be used to estimate treatment comparisons within the subgroups that correspond with the

Date:22FEB2023 Version: Final 2.0 ST/form/010/15 sub-grouping factor. The results from the analysis are to be presented as described above in tables and/or figures. Subgroups of interest include but are not limited to:

- Race (White, Non-White)
- Sex (Male, Female)
- Age group (
- Improvement during the run-in period (Yes, No). Improvement in this case is defined as a 2-point or greater improvement in the total score.
- To identify items which are primarily driving an improvement in CDM1-RS total score, the 11 individual items will each be analysed in an analogous method to the primary estimand above. A forest plot with all 11-items on the y-axis, showing the treatment effect will additionally be provided.
- The occurrence and potential imbalance of intercurrent events (e.g. concomitant medication changes, protocol non-compliance), deaths and COVID-19 impacts between treatment groups will be reviewed after unblinding the randomization.
 - If an imbalance is detected in the intercurrent events, further summaries and/or analyses may be undertaken to assess the impact of this.
 - Deaths are not anticipated during the study. If an imbalance in deaths is determined, a joint rank analysis (based on the change in CDM1-RS from baseline and time to death) may be utilized.

Summaries and Figures

Summary statistics of observed values and change from baseline will be presented by visit and treatment for the in-clinic and telehealth visits separately. For subjects who have both an in-clinic and telehealth assessment at a visit, change from baseline in CDM1-RS will be calculated for both methods and summarised separately.

The observed CDM1-RS total score will be presented over time using by subject line plots by treatment group for the in-clinic and telehealth visits separately. The plots will be presented together but on two separate panels.

Additionally, histograms of the change from baseline at each visit will be presented by treatment group. Empirical cumulative distribution functions (CDFs) of the change from baseline will be presented by treatment group at Visit

The adjusted LS mean changes from baseline and SEs over time will be presented via line plots as estimated by the primary estimand MMRM model by treatment group.

